**Sample Size Estimate.** Accurate effect sizes are difficult to determine given the limited research on the effect of CPAP on APOs. We estimate that initiation of CPAP in the treatment group will reduce their risk of APOs by 20%. Using G\*Power 3.1.9.2 and a one-sided Fisher's exact test with an alpha of 0.05 and power of 80%, and a 2 to 1 allocation of control: treatment group, we would need 55 subjects in the treatment group and 110 in the control group ( $N = 165$ ). Over a 36-month data collection period we originally estimated we could enroll up to 30 subjects per quarter for a total of  $N = 360$  by the end of data collection ( $N = 180$  in each group). Subjects will be randomized to one of the two groups in a 1:1 ratio. Assuming 30% of subjects in the treatment group require CPAP initiation during their pregnancy this will give us at approximately  $N = 55$  subjects who received CPAP during pregnancy and up to  $N = 180$  control subjects. These

enrollment estimates thus meet our sample size calculation and approximate 2:1 allocation plan for analysis.

The sample size estimate of was revised 18 January 2018 and approved by CDR [name]. Our new sample size estimate was based on a 20% difference in adverse pregnancy events would be  $N = 180$  (144 in control group and 36 in treatment [CPAP group]). The plan was to continue enrollment until January 2019. The reason for stopping in January is because of the 9-month follow-up period, which would take us to September 2019. We estimated that we could enroll between 11-14 patients per month which would give us an estimated sample size at the end of active recruitment of  $N = 252$  to 288 subjects (126 to 144 per group). If we assume 25% in the treatment group have OSA, then we estimate we will have 32 to 36 subjects in the treatment group who will require CPAP therapy, meeting our target sample size.

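### The sample size sets CPAP recipients, all selected for OSA, against unselected controls, so the 80% power stated for 55/110 is not assured if untreated OSA raises the risk of adverse pregnancy outcomes

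*Combined protocol and SAP*

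**What the plan says.** All places are in the combined protocol and SAP.

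- **Effect (Sample Size Estimate).** "We estimate that initiation of CPAP in the treatment group will reduce their risk of APOs by 20" per cent. Whether this is absolute or relative is not said, and no APO rate is given for any group.
- **Test and size (same section).** The calculation uses "a one-sided Fisher's exact test with an alpha of 0.05 and power of 80" per cent, with two controls per treated woman, and concludes that "we would need 55 subjects in the treatment group and 110 in the control group".
- **How the ratio arises.** Randomization is equal: "Subjects will be randomized to one of the two groups in a 1:1 ratio". The 2:1 figure comes from "Assuming 30% of subjects in the treatment group require CPAP initiation during their pregnancy", which yields about 55 CPAP recipients, set against up to 180 controls. The section closes: "enrollment estimates thus meet our sample size calculation and approximate 2:1 allocation plan for analysis".
- **Revision of January 2018.** The target becomes 36 in the CPAP group and 144 controls, for a 20% difference in adverse pregnancy events. The 36 is reached with "If we assume 25% in the treatment group have OSA". Power, alpha and sidedness are not restated.
- **Who is in each group (Research Design and Methodology).** Treatment-arm women are referred for possible CPAP when their AHI is at least 5. Controls have no sleep study until 3 months postpartum.
- **Outcome test (Statistical Analysis).** Fisher's exact test compares the treatment group with the control group.

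**The concern.** The stated effect is a change within one kind of patient: a woman with OSA, with CPAP against the same woman without it. The calculation enters it as a difference between two kinds of patient. One group consists only of women with OSA. The other is the full control arm, in which OSA is expected in only a minority.

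The two differences agree only if women with untreated OSA have the same APO risk as the other women enrolled. The title, which proposes CPAP for OSA to reduce APOs, points the other way: if OSA did not raise the risk, treating it would have little to remove.

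Two things are at stake. The power behind 55/110 may be much lower than stated. And if the contrast were used as an analysis, CPAP recipients would start from a higher risk than their comparators, so the result would be biased against CPAP. A useful treatment could look ineffective or harmful. Correcting the sidedness of the test or the allocation ratio would not remove this.

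**Working it through.** **Inputs from the Sample Size Estimate section:** one-sided Fisher's exact test, alpha 0.05; group sizes 55/110 (required), 55/180 (anticipated) and 36/144 (revised); effect 20; share 30% (original) or 25% (revised).

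**Assumptions, because the documents give no figure:** the control APO rate; the excess risk d; the 20% read as 20 percentage points; prev, the OSA share among controls, set equal to the plan's 30% or 25%; and CPAP recipients having the average untreated risk of women with OSA.

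**Step 1: reproduce the plan's figures.** Power is the exact probability of rejection, summed over all pairs of binomial outcomes.

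- 55/110, 40% against 20%: 80.4%. With 54/108 it is 79.4%, so 55/110 is the smallest 2:1 design that reaches 80%. (80% against 60% also gives 55/110, at 80.8%.)
- 36/144, 30% against 10%: 80.0%. With 35/140 it is 78.9%.
- A relative reduction of 20% does not reproduce 55/110: power is 11% to 64% for control rates of 20% to 80%.

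The published sizes thus match a 20-point difference between the two groups with no allowance for OSA.

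**Step 2: the expected contrast.** Let p be the risk without OSA.

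- Control mean: p + prev × d
- CPAP recipients: p + d − 20
- Difference: (p + prev × d) − (p + d − 20) = 20 − (1 − prev) × d

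With prev = 30% this is 20 − 0.70d; with prev = 25% it is 20 − 0.75d. At d = 10 the contrast is 13 or 12.5 points; at d = 20 it is 6 or 5 points.

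**Step 3: power with that contrast,** one-sided, alpha 0.05, control rate held fixed.

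| Groups | Control rate | prev | d = 0 | d = 5 | d = 10 | d = 15 | d = 20 |
|---|---|---|---|---|---|---|---|
| 55/110 | 40% | 30% | 80% | 63% | 44% | 27% | 15% |
| 55/110 | 30% | 30% | 90% | 73% | 51% | 30% | 16% |
| 55/110 | 50% | 30% | 75% | 58% | 41% | 25% | 14% |
| 55/180 | 40% | 30% | 86% | 69% | 49% | 30% | 16% |
| 36/144 | 30% | 25% | 80% | 58% | 37% | 20% | 10% |

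There is some slack where the control rate is lower or the control group larger. At a 30% control rate, 55/110 still has 81% at d = 3. At a 40% control rate, 55/180 has about 80% at d = 2.

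**Step 4: sensitivity to the OSA share.** If prev were 50%, 55/110 at a 40% control rate and d = 10 would have a contrast of 20 − 0.50 × 10 = 15 points and 55% power, against 44% at prev = 30%.

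**Step 5: bias if the contrast is analysed.** The shift against CPAP is (1 − prev) × d: 7 to 7.5 points at d = 10 and 14 to 15 at d = 20. With d = 20 and a true benefit of 10 points, the expected difference is 10 − 14 = −4 or 10 − 15 = −5, so CPAP would look harmful.

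**The case against.** Several counter-arguments have force.

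- **The 80% is tied only to 55/110.** This is correct. The revision states no power, and its 80% here follows from assuming a 30% control rate.
- **The revision's 20% may be a net difference between the two listed groups.** This is a fair reading, since that paragraph does not speak of the CPAP women's own risk. Power then holds by definition, but CPAP would have to lower risk by 20 + (1 − prev) × d points (27.5 at d = 10, prev 25%), which is not justified anywhere.
- **d is unknown.** This stands. Every woman enrolled carries a risk factor for OSA, such as obesity, chronic hypertension or prior preeclampsia, so controls are not a low-risk group and the excess could be small.
- **The original 30% is the share requiring CPAP, not the share with OSA.** This also stands. CPAP is only possible after referral, so the OSA share may be higher. The loss of power is then smaller, though still large at 50%.
- **The outcome test already compares the randomized groups.** True, so the bias arises only if the 2:1 contrast is carried out. But the Sample Size Estimate section does call it a plan for analysis.

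A reader might infer that 80% power holds only if OSA carries no excess risk at all, or that the true contrast is 5 to 6 points. The documents support neither. The first fails wherever there is slack, as Step 3 shows. The second needs a 20-point excess that CPAP removes entirely, and no rate in the documents establishes that.

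**Conclusion.** The concern holds as a fault in an unstated assumption, not in arithmetic: 55/110 is computed correctly for a 20-point difference, but the effect described is not the difference between the groups described. Once OSA carries a material excess risk, as the trial's rationale implies, 80% is not assured. For d = 10, power at 55/110 is 41% to 51% over control rates of 30% to 50% with prev 30%; for 36/144 it is 37% at a 30% control rate with prev 25%. An excess of only 2 or 3 points would do little harm at some control rates.

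These sizes rest on assumed values of the control rate, d and prev, and on an absolute reading of the 20%. The direction does not depend on the exact values: for any d above zero and OSA share below 100%, the expected contrast is smaller than the stated effect on CPAP women. The harm to inference is conditional on the 2:1 contrast being used as an analysis.

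**What to change.** In the Sample Size Estimate section:

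1. Withdraw the unqualified 80% power for 55/110, and do not present 36/144 as adequate.
2. State the assumed control APO rate, the OSA share (kept distinct from the share requiring CPAP) and d. Say whether 20% is absolute, and whether the revision's 20% is a within-OSA effect or a net difference.
3. Give the expected contrast, 20 − (1 − prev) × d, and show power over a range of d, for example 0 to 20 points.
4. Delete the 2:1 allocation plan for analysis, so that the test of APOs is the comparison of all randomized women already given under Statistical Analysis. Label any comparison of CPAP recipients with all controls as exploratory and confounded by OSA.

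The cost is rewording and a less favourable stated power. Enrolment does not change.

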Subjects in the treatment group completed an OSA pregnancy screening questionnaire at each time point. The questionnaire collects information on general work and sleep patterns, sleep habits, snoring and sleep apnea symptoms, and STOP-BANG score. A research coordinator drove to the patient's home to set-up the unattended sleep study at each time point with the Watch-PAT-200 devices. The next day the research coordinator picked-up the device. Watch-PAT data was downloaded on a password-protected password and analyzed with the WatchPat zzzPAT proprietary software which automatically scored the results. If there was a technical error with the sleep study the research coordinator attempted to reschedule completion of the sleep study.

The Watch-PAT-200 is an FDA-approved portable diagnostic device (6 channels: peripheral artery tone, pulse rate, oxygen saturation, actigraphy [to calculate sleep stages], body position, & snoring) used for screening, detection, and the follow-up treatment of OSA. It uses peripheral artery tonometry (PAT) finger plethysmography and standard oxygen saturation (SPO2) probe, which allows for recording of the PAT signal, heart rate, and SPO2. Sleep time is estimated with

actigraphy. Specific data obtained included: sleep stages, pRDI, pAHI, pODI (peripheral artery tonometry respiratory disturbance index [pRDI], apnea hypopnea index [pAHI], and oxygen desaturation index [pODI]), mean and lowest oxygen saturation, percent sleep time with  $\text{SPO}_2 < 90\%$ ,  $< 88\%$ ,  $< 85\%$ ,  $< 80\%$ , and  $< 70\%$ , percent rapid eye movement of sleep time (% of sleep in REM), and the mean, minimum, and maximum heart rate.

Subjects with an  $\text{AHI} \geq 5$  were referred to the sleep medicine department for evaluation and possible treatment with CPAP. Those subjects referred for to sleep medicine received education on OSA and treatment options. If CPAP was ordered a contracted durable medical equipment company representative contacted the subject and coordinated delivery and set-up of the CPAP device. Devices used were the AirSense 10 AutoSet with auto-titrated pressure ranging from 5 to 15 cm  $\text{H}_2\text{O}$ . CPAP compliance data was obtained from the durable medical equipment contractor. CPAP compliance defined as  $> 4$  hours/night for 70% of nights.

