The primary outcome was the difference in APOs between the two groups. After delivery the research coordinator reviewed the medical records and recorded the rate of individual and composite APOs in both groups (defined as a composite variable which included gestational hypertension, preeclampsia, eclampsia, gestational diabetes, preterm birth, low birth weight, or stillbirth). Results were confirmed with a co-investigator who was a Maternal Fetal Medicine Obstetrician. Secondly, we examined the rate and trends in OSA in early and late pregnancy, and at 3 months postpartum (between 8 and 12 weeks), and differences in hospital costs at the time of delivery. An exploratory aim was to compare differences in APOs between subjects at high risk for OSA started on CPAP therapy in either early or late pregnancy.

Upon completion of the 3-month postpartum sleep study subjects were given a \$150 Target gift card.

**Statistical Analysis.** Descriptive and inferential statistics were used to analyze the results. A Fisher's Exact test was used to compare differences in APOs between the treatment and control group. If significant differences are found in APOs a multiple logistic regression control for significant covariates and CPAP usage. Because sleep study results were not normally distributed a Friedman's test was used to analyze differences in sleep study results at the three time points. If significant differences are found in sleep study results a post hoc Wilcoxon Ranked Sign test will be used to compare differences at individual time points. Differences in hospital costs at the time of delivery were analyzed with a  $t$ -test. A  $P < .05$  was considered significant.

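### The only stated power (80%) is for CPAP-treated women against controls; none is given for the 1:1 randomized comparison that the primary Fisher test makes

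*Combined protocol and SAP*

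**What the plan says.** The Research Design and Methodology section defines the treatment group as everyone randomized to sleep studies during pregnancy. Women with an AHI of 5 or more "were referred to the sleep medicine department for evaluation and possible treatment with CPAP". Controls have no sleep study until 3 months postpartum.

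The primary contrast is stated plainly: "The primary outcome was the difference in APOs between the two groups". The Statistical Analysis paragraph adds: "A Fisher's Exact test was used to compare differences in APOs between the treatment and control group". The threshold is P < .05, with no sidedness given.

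On allocation, the Sample Size Estimate section says "Subjects will be randomized to one of the two groups in a 1:1 ratio". It ties the effect to CPAP: "We estimate that initiation of CPAP in the treatment group will reduce their risk of APOs by 20" per cent, without saying whether that is absolute or relative. For a one-sided Fisher test at alpha 0.05 with 80% power, "we would need 55 subjects in the treatment group and 110 in the control group". It then meets the 55 by taking 30% of a 180-woman treatment arm as CPAP starters.

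The January 2018 revision gives "144 in control group and 36 in treatment [CPAP group"] and restates no power, alpha or sidedness. It expects 126 to 144 women per arm and reaches its target this way: "If we assume 25% in the treatment group have OSA, then we estimate we will have 32 to 36 subjects in the treatment group".

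**The concern.** The contrast that was sized is not the contrast that is tested. The 55 and the 36 are a subset of the treatment arm, while the primary test uses the whole arm. If the benefit comes through CPAP and only 25-30% of the arm starts it, the arm-level difference is a fraction of the effect used for sizing.

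The sized contrast is also not a randomized one. CPAP-treated women are selected after randomization by a positive sleep study. Controls are not tested during pregnancy, so they mix women with and without OSA.

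What is at stake is how a null result is read. The only power in the document is 80%, so a reader could take a non-significant primary test as evidence that screening plus CPAP does not help. The regression that adjusts for CPAP usage is planned only if APOs differ significantly, so the primary test also decides whether that analysis is run.

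**Working it through.** **Inputs from the plan.** Effect 20%; CPAP share of the treatment arm 30% (original) and 25% (revised); arms of 180 (original) and 126-144 (revised); one-sided alpha 0.05 in the sample-size section and P < .05 without sidedness in the analysis section.

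**Assumptions.** Control APO rate 30-60%, scanned in 5-point steps because none is stated; no benefit in women without CPAP.

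**Method.** Exact power = sum over all (x_t, x_c) of Bin(x_t; n_t, p_t) x Bin(x_c; n_c, p_c) x 1{Fisher P < 0.05}.

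**1. Who the 55 and 36 are.** 0.30 x 180 = 54, close to 55. 0.25 x 126 = 31.5 and 0.25 x 144 = 36, which is the plan's 32 to 36. Both targets are counts of women on CPAP.

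**2. The plan's own figure.** Without a control rate it cannot be reproduced outright, but it can be tested for consistency.
- 55 versus 110, one-sided, 20 absolute points: 80.4% for 40% versus 20%; 73-90% over control rates of 30-60%.
- 55 versus 110, one-sided, 20% relative: 16-36%. The absolute reading therefore fits the stated size.
- 36 versus 144, one-sided, 20 absolute points: 80.0% at a 30% control rate, 69.3% at 40%, 63.2% at 60%. The two sizes imply different unstated control rates.

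**3. Expected difference between arms** = CPAP share x effect in CPAP users.
- Original: 0.30 x 20 = 6 points.
- Revised: 0.25 x 20 = 5 points.

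**4. Power of the randomized Fisher test**

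| Plan | Arm difference | One-sided | Two-sided |
|---|---|---|---|
| Original, 180 per arm | 6 points | 27-32% | 18-21% |
| Revised, 126 per arm | 5 points | 16-19% | 10-12% |
| Revised, 144 per arm | 5 points | 19-20% | 11-13% |

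At a 40% control rate (one-sided / two-sided): 180 per arm, 40% versus 34%, 28.2% / 18.9%; 126 per arm, 40% versus 35%, 17.4% / 10.3%; 144 per arm, 40% versus 35%, 18.7% / 11.5%.

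**5. Sensitivity**
- *20% relative.* The arms then differ by 0.25 x 20% = 5% relative (revised) or 0.30 x 20% = 6% relative (original), if CPAP users share the arm's average risk. Revised: 6-11% one-sided, 4-6% two-sided. Original: 8-14% and 5-9%.
- *Partial uptake.* If three quarters of the 25% start CPAP, the difference is 0.25 x 0.75 x 20 = 3.75 points. At a 40% control rate, power is 13-14% one-sided and 7-8% two-sided.
- *Whole arm gains 20 points.* 87-99% two-sided with 126-144 per arm.

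**6. What 126-144 per arm can show**
- Smallest difference with 80% power, in 0.5-point steps, at a 40% control rate: 14.5-15.5 points one-sided, 16-17.5 two-sided. Over 30-60%: 13.5-17 and 14.5-18.5.
- 95% CI half-width = 1.96 x sqrt[p_t(1-p_t)/n + p_c(1-p_c)/n]. The narrowest case (144 per arm, 30% versus 25%) is 1.96 x sqrt[(0.21 + 0.1875)/144] = 10.3 points. The widest (126 per arm, 50% versus 45%) is 1.96 x sqrt[(0.25 + 0.2475)/126] = 12.3 points.

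**The case against.** The strongest reply is that the sponsor may have meant to compare CPAP-treated women with controls. The sample-size section refers to a roughly 2:1 allocation for its analysis, and the revision labels the smaller group as CPAP. On that reading the size matches its intended contrast. This confirms what was sized, but it does not rescue the plan. The analysis text never names that comparison as primary, secondary or exploratory (the exploratory aim concerns CPAP started early or late in pregnancy), and the comparison is not randomized. The two sections would still have to be reconciled.

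A second reply is that the 20% might apply to the whole arm, which would leave the trial well powered. The text speaks against it: the effect is attributed to starting CPAP, and the 30% and 25% steps would serve no purpose, since 180 per arm already exceeds 55 versus 110.

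Third, the low powers rest on a control rate the plan does not give and on no benefit without CPAP, although referred women also receive education on OSA and treatment options. That stands. The figures are conditional and show the size of the problem. The absence of any arm-level power is a fact of the text and needs none of these assumptions.

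Finally, the randomization and the primary test remain valid, type I error is unaffected, and planned enrollment ended in January 2019. That also stands, which is why the remedy concerns reporting.

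**Conclusion.** The concern holds and must be fixed. The 80% power belongs to a contrast of women selected after randomization, and the plan states no power for the comparison its primary test makes. That much rests on the text alone.

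On the plan's own effect and uptake figures, and under the assumptions set out in the check, power for the randomized comparison is roughly a fifth or less under the revised plan and a third or less under the original. If CPAP works as assumed, a non-significant primary result is then about 80-90% likely (revised) or 68-82% likely (original). The relative reading makes this worse. Under the absolute reading, a higher baseline risk in women with OSA does not change the 5- or 6-point difference. Only the whole-arm reading removes the problem, and the text does not favour it.

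**What to change.** - State in the Statistical Analysis paragraph that the primary analysis compares all randomized women by assigned arm.
- Label 55 versus 110 and 36 versus 144 as sizes for a non-randomized CPAP-versus-control comparison. Keep them as the record of how the size was chosen, but not as the power of the primary test.
- Put a conditional statement in place of the 80% as the power of the primary test, for example: *If CPAP lowers APO risk by 20 absolute points, 25% of the treatment arm starts CPAP, women without CPAP do not benefit, and the control APO rate is 30-60%, the randomized comparison with 126-144 per arm has about 16-20% power (one-sided) or 10-13% (two-sided). At a 40% control rate, the difference detectable with 80% power is 14.5-15.5 points (one-sided) or 16-17.5 points (two-sided).*
- Name the sidedness actually used for the primary test.
- Report the risk difference with its confidence interval as the main result, and state that a non-significant result will not be read as no effect.

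The cost is wording in two sections and a much less favourable stated power. This corrects the reporting; it does not restore power, and no extra enrollment is proposed.

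### The revised sample size paragraph says that 32 to 36 CPAP subjects meet the 36/144 target, but by its own figures only the top of the range (N=288) does

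*Combined protocol and SAP*

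**What the plan says.** All the figures are in the Sample Size Estimate section.

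- **Original calculation.** It assumed that "initiation of CPAP in the treatment group will reduce their risk of APOs by 20" per cent, used a "one-sided Fisher's exact test with an alpha of 0.05 and power of 80" per cent, and arrived at 55 CPAP subjects and 110 controls.
- **Revised target (18 January 2018).** "Our new sample size estimate was based on a 20% difference in adverse pregnancy events", giving N=180, split as "144 in control group and 36 in treatment [CPAP group". The test, its direction, alpha and power are not restated.
- **Revised projection.** Recruitment is expected to end at 252 "to 288 subjects (126 to 144 per group". With 25% of the treatment group assumed to have OSA, the paragraph concludes: "we estimate we will have 32 to 36 subjects in the treatment group who will require CPAP therapy, meeting our target sample size".

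The Research Design and Methodology section says that women with an AHI of 5 or more were sent to sleep medicine, where CPAP might or might not be ordered. The Statistical Analysis section compares the treatment and control groups with Fisher's exact test.

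**The concern.** The closing statement covers the whole projected range, yet its lower value, 32, is below the target of 36. The control group has the same problem: the projection starts at 126 and the target is 144. A reader who takes the sentence at face value will believe that any enrolment between 252 and 288 delivers the planned size. This is the only assurance in the document that the revised trial is large enough for its CPAP comparison. The text also gives too little for a reader to work out the power at the lower end.

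**Working it through.** **Inputs, all from Sample Size Estimate:** total N of 252 to 288; 1:1 randomization; 25% of the treatment group with OSA; target of 36 CPAP subjects and 144 controls.

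**1. Reproduce the projection.** Controls = N/2 and CPAP subjects = 0.25 × N/2.

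- N=252: controls 126; CPAP 0.25 × 126 = 31.5, printed as 32.
- N=288: controls 144; CPAP 0.25 × 144 = 36.

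The printed range of 32 to 36 is therefore correct arithmetic.

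**2. Compare with the target.**

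| N | CPAP (target 36) | Controls (target 144) | Total (target 180) |
|---|---|---|---|
| 252 | 32, short by 4 (11%) | 126, short by 18 (12.5%) | 158, short by 22 |
| 288 | 36, met | 144, met | 180, met |

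**3. Smallest sufficient N.** Setting 0.25 × N/2 ≥ 36 gives N ≥ 288, and N/2 ≥ 144 also gives N ≥ 288. The largest enrolment projected is thus the smallest that suffices, for both groups.

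**4. Reserve at N=288.** It is zero. The projection counts every woman with OSA as a CPAP subject, whereas the methodology section makes CPAP conditional on the sleep medicine evaluation. One such woman not starting CPAP gives 35/144, and one control lost gives 36/143. Neither uptake nor loss is quantified in the plan, so the likely shortfall cannot be sized.

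**5. Illustrative power.** The control-group rate is not stated, so the rates below are assumptions. The test settings are those of the original calculation (one-sided Fisher, alpha 0.05), assumed to carry over. Power is exact: the summed probability of all pairs of binomial outcomes with a one-sided Fisher p-value of at most 0.05.

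| Control vs CPAP rate | Reading of 20% | 36/144 | 32/126 |
|---|---|---|---|
| 25% vs 5% | absolute | 89.5% | 84.8% |
| 30% vs 10% | absolute | 80.0% | 74.8% |
| 40% vs 20% | absolute | 69.3% | 64.2% |
| 60% vs 40% | absolute | 63.2% | 57.8% |
| 90% vs 70% | absolute | 82.7% | 78.3% |
| 30% vs 24% | relative | 12.1% | 11.3% |
| 80% vs 64% | relative | 54.4% | 49.9% |

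At 30% vs 10% with four controls per CPAP subject, 36/144 is the first size to reach 80%, so the target is attainable under the original settings. In the absolute rows the lower end costs about 4 to 5 percentage points of power. The level itself depends heavily on the rate and scale that the plan leaves out.

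**The case against.** The strongest reply is that the sentence hides nothing. Target and range are printed side by side, the section is loosely worded elsewhere (0.30 × 180 = 54 is rounded up to about 55), and the illustrative cost is about 5 points of power. Moreover, the power concerns CPAP recipients against controls, whereas the stated primary test compares the randomized groups, projected at 126 to 144 each. Most of this stands, and it keeps the point minor. The comparison with the original projection helps the plan less: 54 was one short of 55 but came with up to 180 controls against 110 needed, while the revised lower end is short in both groups.

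Three stronger readings are tempting and are not supported.

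- **That no inputs are given for 36/144.** The revision states a 20% difference and the split, and the same section gives test, direction, alpha and power for the original calculation. It is natural to carry these over. Missing throughout are the control-group rate and the scale of the 20%.
- **That 36/144 is miscalculated, or that an input was changed silently.** With an absolute 20 points, one-sided, 30% vs 10% yields 36/144, while 40% vs 20% or 80% vs 60% yields 55/110, which might suggest a changed control rate. But the revision calls itself new, and its wording moves from a reduction in risk to a difference. If the first is read as relative and the second as absolute, both sizes give about 80% power at one control rate: 79.7% and 79.8% at 88% one-sided, or 80.3% and 79.8% at 90.25% two-sided. The text cannot settle the matter.
- **That a particular monthly enrolment is needed.** This requires the number already enrolled at the revision, which is not stated.

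**Conclusion.** The claim that the projection meets the target is true only at its upper bound. At N=252 the plan's own figures give 32/126 instead of 36/144, and N=288 reaches the target with nothing in hand. This part rests on the plan's arithmetic alone. The loss of power, 80% to 75%, is an illustration that assumes 30% vs 10% and the original test settings. It applies to CPAP recipients versus controls, so a reader should not infer that the randomized comparison loses this amount. Severity: minor. The statement is wrong as written, but the correction changes neither design nor enrolment.

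**What to change.** Replace the closing claim of the revised paragraph with a statement that 36 CPAP subjects and 144 controls are reached only at N=288, with full CPAP uptake and no loss, and that N=252 gives about 32 and 126.

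Report the power at 32/126, with the control-group rate used, whether the 20% is absolute or relative, and whether the original test, direction and alpha were kept. Say that this power is for CPAP recipients versus controls and not for the randomized comparison in the Statistical Analysis section.

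The cost is a less favourable stated size and power. No extra enrolment is required.
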